21.0 Potential Benefits to Participants

PROTOCOL TITLE: iThrive WI – A smartphone intervention for overdose and risk and COVID-19 among people who use drugs

21.1 Participating in this study may be a beneficial way for PWID to get support from other people living with substance use problems. Thrive4Life Connect will also provide participants with information about local resources and harm reduction. The study may also benefit other people in the future by helping us learn more about how a smartphone app can lower overdose risk for people who use drugs.

22.0 Risks to Participants

22.1 Risks:

- Information participants enter into Thrive4Life Connect can be viewed by UW and Vivent Health research team members. They may monitor discussion boards and post information there. Study staff will also reach out to participants via private messaging or other contact methods (texts, phone calls, social media, etc.). Information participants enter into Thrive4Life Connect is not stored on the phone, but this information is stored on the Thrive4Life Connect app.
- When participants set up their Thrive4Life Connect account, they will be asked to create an account username. This username will be listed on discussion board posts and included in a list of participants that can receive private messages. To reduce the risk of being identified, we will require participants to choose a username that will NOT include any identifiable information such as their first name, last name, date of birth, address, etc.
- Other participants can see what is posted to the discussion boards. There is a risk that other participants could identify each other based on the information they provide in their discussion board posts.
- Answering questions on sensitive issues (like drug and alcohol use, mental health, etc.) in surveys may cause anxiety, distress, embarrassment, or feelings of sadness. Participants do not have to answer any questions that they do not want to.
- The Thrive4Life Connect app allows participants to share their views, opinions, photos, and personal experiences. However, participants are NOT allowed to post content on the Thrive4Life Connect app that promotes racism, bigotry, hatred, nudity, or physical harm of any kind against any group or individual. If a participant uses the app in an inappropriate or illegal manner, the research staff will delete the inappropriate content and follow up with them. If the behavior continues, the research staff may withdraw the participant from the study.

PROTOCOL TITLE: iThrive WI – A smartphone intervention for overdose and risk and COVID-19 among people who use drugs

- There is a risk that study participants may send or receive private messages including unwanted or inappropriate content. If this happens, we ask that participants report this information to the study team [contact]).
- Information from the internet and/or Thrive4Life Connect discussion boards could be wrong. However, a panel of UW staff review all information on the app, so this risk is unlikely. We will provide tips to help participants figure out whether they can trust the information they receive from these sources.
- There is a risk that participant information could become known to someone not involved in this study. If this happens, it could result in damage to reputation, which could also affect relationships with family and friends, affect employment, or make it harder to get insurance or a job.
- The study team may discover behavior that raises concern about harm to themselves or others. If we see anything that suggests that a participant or others face imminent risk of harm, we will contact appropriate parties to intervene (e.g., your care team and/or police).

22.2 Potential participants may choose not to participate or enroll after learning more about the study. Participants may end their participation at any time and choose not to answer any questions they do not wish to. Participants are not required to use the app discussion board. They must be able to receive private messages or texts from study staff (with survey reminders and weekly intervention content feedback) but are not required to respond. Participants will be shown how to add a password to their study iPhone, and how to disable the function that shows a preview of the content received in messages during study enrollment to protect privacy.

23.0 Provisions to Monitor the Data to Ensure the Safety of Participants

23.1 The study team (lead researchers [name] and [name] and staff including [name], [name], and [name]) will be responsible for monitoring the data to ensure the safety of participants. We will review all survey data collected at baseline, 3 months and 6 months for any reports of serious events (i.e., death, life-threatening overdose, hospitalizations lasting 24 hours or more). Data will be monitored on a monthly basis. We will also review any reports of potentially serious events received by participants to the study team via the Thrive4Life Connect app private message function or discussion board on a rolling basis. Given the sample size of only 60 participants and

PROTOCOL TITLE: iThrive WI – A smartphone intervention for overdose and risk and COVID-19 among people who use drugs

planned analyses focused on feasibility, we will not be able to statistically examine the safety data to determine whether harm is occurring. We will review adverse events starting with recruitment of the first study participant through 30 days after the last date that the final participant completed their final study procedure (i.e., all 6 months surveys).

The severity of each event will be classified using the following guidelines adapted from the UW-Madison ICTR Trial Template:

Mild (Grade 1)	Events require minimal or no treatment and do not interfere with the subject's daily activities.
Moderate (Grade 2)	Events result in a low level of inconvenience or concern with the therapeutic measures. Moderate events may cause some interference with functioning.
Severe (Grade 3)	Events interrupt a subject's usual daily activity and may require systemic drug therapy or other treatment. Severe events are usually potentially life-threatening or incapacitating.
Life Threatening (Grade 4)	The subject was at risk of death at the time of the event.
Fatal (Grade 5)	The event caused death.

The relationship of each event to study procedures will be classified using the following guidelines adapted from the UW-Madison ICTR Trial Template:

Definitely Related	Clearly related to the study procedures/intervention and other possible contributing factors can be ruled out.
Probably Related	Likely related to the study procedures/intervention and the influence of other factors is unlikely.
Possibly Related	Possibly related to the study procedures/intervention and there are other factors that could be equally likely.
Unlikely to be related	Doubtfully related to the study procedures/intervention and there is another likely cause.

PROTOCOL TITLE: iThrive WI – A smartphone intervention for overdose and risk and COVID-19 among people who use drugs

Unrelated	Clearly not related to the study procedures/intervention and/or evidence exists that the event is definitely related to another cause.
-----------	--

The event will be considered unexpected if the nature, severity, or frequency of the event is not consistent with the risk information previously described in the protocol, the IRB application, or the informed consent document.

In consultation with the lead researchers, a trained member of the study team will be responsible for conducting an evaluation of adverse events or unanticipated problems and shall report these issues and evaluation to the reviewing Institutional Review Board (IRB) in accordance with the Reportable Event Reporting Requirements.

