4.0 Number of Participants

4.1 This study will include 60 participants in total across 3 Vivent Health syringe services locations in Wisconsin – Milwaukee, Appleton, and Eau Claire.

- Milwaukee: 30 participants
- Appleton: 15 participants
- Eau Claire: 15 participants

4.2 In a prior longitudinal study with Vivent Health (WI Rural Opioid Initiative - Intervention phase), we have experienced up to 50% attrition at 3 months and 6 months. Because of this, we may enroll up to 90 participants in this study.

4.3 Enrolled participants are individuals who complete the baseline survey. Participants who leave the study early (i.e., before completing the 3-month study assessment) may be replaced.

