8.0 Consent/Accent Process

PROTOCOL TITLE: iThrive WI – A smartphone intervention for overdose and risk and COVID-19 among people who use drugs

8.1 This study will involve individuals who are using drugs, who may also be receiving inpatient or outpatient services for mental illness, developmental disability, or alcohol and other drug abuse (AODA). To minimize the risks to this population, participants will be provided with a paper or electronic copy of the informed consent when they initially screen as eligible to participate in the study. The informed consent process will be completed at the enrollment visit by either watching a video of the informed consent highlights then discussing with a Prevention Specialist OR by discussing the key areas of the informed consent with a Prevention Specialist. Participants will be informed that their participation is voluntary, they can stop participating at any time, and they can skip any survey questions they are uncomfortable answering. After watching the informed consent video or walking through the consent with a Prevention Specialist, participants will be prompted to ask the research team any questions. We also obtained a Certificate of Confidentiality from the National Institutes of Health, which participants will be made aware of.

Walkthrough of Study Informed Consent Process:

Participants will first complete a screening survey to determine their eligibility. This screener will be completed with Prevention Specialists at participating Vivent Health locations. Eligible participants who are interested in participating in the study will be invited to complete a locator form with Prevention Specialists asking for multiple contact methods, which will be utilized for follow-up throughout the study. Participants that express interest in enrolling in the study will be invited back to Vivent Health in one week for an enrollment and informed consent appointment. Participants will be given a paper or electronic copy of the study consent form and asked to review this information in the week before their enrollment appointment.

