The study meets the criteria for a waiver of signed consent through criteria set #1 on HRP-411. The research involves explaining a written script of the informed consent through a pre-recorded video that covers the elements of consent in HRP-314. Participants will also be able to talk through the informed consent document with a Prevention Specialist if they prefer. Prevention Specialists will be provided with a written script of the informed consent as well. Participants will have the opportunity to ask questions and will receive a paper or electronic copy of the consent to review during the video or discussion and afterwards. The research proposed in this study presents no more than minimal risk of harm to prospective subjects. Regarding the risk to participants, the primary risks include being identified as a participant in this study and distress caused by answering questions about sensitive topics, such as substance use. These risks have been minimized by the study team by having a Certificate of Confidentiality, ensuring that participants are encouraged to password-protect their study iPhone, and ensuring participants do not include any identifiable information in their Thrive4Life Connect public usernames. Study data will also be stored on HIPAA compliant servers at the UW School of Medicine and Public Health. Participants are also free to skip questions they are uncomfortable with answering and can reach out to study staff as needed.

This study also involves no procedures for which written consent is normally required outside of the research context, as we ask participants to download an app available through the app store and participate in self-help type activities.

- 9.2 Participants will be provided with a paper or electronic copy of the informed consent detailing the study procedures, risks, and benefits. They will be asked to review this information during the week

PROTOCOL TITLE: iThrive WI – A smartphone intervention for overdose and risk and COVID-19 among people who use drugs

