13.2 Schedule of Procedures and Study Outline

This study will involve required and optional procedures.

Required activities include:

- Thrive4Life Connect
- Surveys
 - Baseline survey
 - 12 weekly check-in intervention surveys about overdose prevention
 - 3-month survey
 - 9 daily check-in surveys
 - 6-month survey
- Surveys will collect information about: Name, age, gender identity, ZIP code, race and ethnicity, education, marital status, alcohol and drug use, types of health care received, mental health, and other related items.
- Private messaging: Study staff will send participants messages in Thrive4Life Connect to remind participants about when surveys open, send personalized resources, and answer any questions.

PROTOCOL TITLE: iThrive WI – A smartphone intervention for overdose and risk and COVID-19 among people who use drugs

- Data linkage to databases like the Wisconsin Immunization Registry, Medicaid, and Wisconsin hospitalization, emergency medical services, and infectious disease surveillance registries.

Optional activities include:

- Interactive modules about COVID-19 vaccines
- Sharing thoughts on discussion boards and private messaging others
- Engaging with online and local resources in the app
- Logs for motivation and thoughts of gratitude
- Using UW-Madison study team contact information.

See the study timeline/flowchart below for a detailed overview of when various activities will occur.

PROTOCOL TITLE: iThrive WI – A smartphone intervention for overdose and risk and COVID-19 among people who use drugs

13.3 After recruitment, study participants will be involved in the following procedures: eligibility screening, informed consent and study enrollment, baseline surveys, 12-week intervention session, 3-month follow-up surveys, and 6-month follow-up surveys.

PROTOCOL TITLE: iThrive WI – A smartphone intervention for overdose and risk and COVID-19 among people who use drugs

Recruitment, screening for eligibility, and informed consent and enrollment will follow the procedures previously described (See “Recruitment” and “Informed Consent” sections).

During the initial enrollment appointment and after providing informed consent, participants will complete the baseline survey and first of three daily check-ins (ecological momentary assessments).

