We may use identifiable information from participants to link their information to databases like the Wisconsin Immunization Registry, Medicaid enrollment and claims data managed by the UW-Institute for Research on Poverty (IRP), and Wisconsin hospitalization data

PROTOCOL TITLE: iThrive WI – A smartphone intervention for overdose and risk and COVID-19 among people who use drugs

from the Wisconsin Hospital Association Info Center, emergency medical services from the Wisconsin Ambulance Run Data System, and infectious disease surveillance registries capturing COVID-19, hepatitis C, and HIV infections. The purpose of this linkage is to understand how people who inject drugs use health care resources as well as to gather outcome data such as COVID-19 infection or vaccination status, overdose events, and substance use or other treatment utilization. To accomplish this, we will link multiple datasets using individual identifiers (name, date of birth, address, sex, race, phone number).

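### Section 23.1 lists death as a serious event to review, but its named sources cannot reliably show a death, and no visible section adds a vital-status check or names a death record

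*Combined protocol and SAP*

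**What the plan says.** Section 23.1 names two sources for safety review. The first is the study surveys: "We will review all survey data collected at baseline, 3 months and 6 months for any reports of serious events (i.e., death, life-threatening overdose", with hospital stays of 24 hours or more completing the list. The second is reports of possibly serious events "received by participants to the study team via the Thrive4Life Connect app private message function or discussion board on a rolling basis". The severity scale has a fatal grade, and adverse event review runs until 30 days after the last participant's final procedure.

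Other sections bear on the point:

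- **4.2:** in a prior study with the same organisation, "we have experienced up to 50% attrition at 3 months and 6 months", and for that reason "we may enroll up to 90 participants in this study".
- **8.1 and 13.4:** eligible people complete a locator form "asking for multiple contact methods, which will be utilized for follow-up throughout the study", and two or more points of contact are recorded.
- **13.2:** the required activities include "Data linkage to databases like the Wisconsin Immunization Registry, Medicaid, and Wisconsin hospitalization, emergency medical services, and infectious disease surveillance registries".
- **13.3:** the wording becomes permissive: "We may use identifiable information from participants to link their information to databases like the Wisconsin Immunization Registry". The purposes given are health care use and outcome data, including overdose events. The Medicaid and state health department approvals are sought after recruitment ends.
- **20.6:** reported reasons for missing data are tracked, with an open list of examples that does not include death. Carrying the last value forward is allowed.

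**The concern.** The plan says it will review deaths but relies on sources that need someone to report them. The people for whom those sources are silent are the ones lost to follow-up, and a death is one possible reason for being lost.

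Three things are at stake. First, a final statement that no deaths occurred would cover both people known to be alive and people whose status nobody checked. Second, 23.1 judges whether an event is unexpected partly by its frequency and sends its evaluation to the IRB; both steps depend on the event having been found. Third, an undetected death before the 3-month assessment would look like ordinary dropout, and 4.3 allows that person to be replaced.

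**Working it through.** **Step 1. Which planned source could show a death?**

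- *Baseline, 3- and 6-month surveys (23.1).* These are self-completed. They can report the respondent's overdose or hospital stay, but not the respondent's death.
- *App messages and discussion board (23.1).* These show a death only if another person mentions it. Under 22.2, participants need not use the board or answer staff messages.
- *Locator contacts (8.1, 13.4) and staff outreach by text, phone or social media (22.1).* These could establish vital status, but no visible section directs staff to use them for that purpose after a missed survey.
- *Record linkage (13.2, 13.3).* Immunization, Medicaid, hospital, ambulance and infection data are named. No death record is named, although the list is open-ended. Hospital, ambulance or Medicaid data might show some deaths. Section 23.1 does not mention linked data.
- *Reasons for missing data (20.6).* Only reported reasons are tracked, so a death that nobody reports leaves no entry.

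No source in this list is both able to show a death reliably and tied to the safety review.

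**Step 2. For how many people could the survey source be silent?**

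Inputs: attrition of up to 50% in the prior study, planned enrolment of 60 and possible enrolment of up to 90 (all from 4.1 and 4.2).

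No survey at a given visit = attrition × enrolled.

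- 0.50 × 60 = 30
- 0.50 × 90 = 45

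These are upper-end counts of missing surveys, not of missed deaths. Some of these people may still be seen in the app or at the site.

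**Step 3. Is it plausible that any death occurs?**

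The documents give no mortality rate, so this step is an assumption for scale only and the conclusion does not rest on it. For an assumed 6-month risk of death p among N enrolled, the chance of at least one death is 1 − (1 − p)^N:

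| Assumed p | N = 60 | N = 90 |
|---|---|---|
| 0.5% | 26% | 36% |
| 1% | 45% | 60% |
| 2% | 70% | 84% |
| 3% | 84% | 94% |

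These are chances that a death occurs, not that one is missed. The second would need a detection rate, which the documents do not give either.

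**The case against.** The strongest reply is that deaths may well come to light anyway. Participants are mainly clients of the sites, payment is normally collected there, and the site's research supervisor is on the study team. Section 23.1 keeps adverse event review open past the last survey, and a death learned of through a site would fall within the evaluation and IRB reporting process. The linkage covers overdose events without restricting them to non-fatal ones, and its open list does not exclude death records. Requesting it after recruitment is no weakness for a retrospective check.

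This stands in part. It means a reader should not infer that deaths are likely to be missed: the documents give neither a mortality figure nor a detection rate, and 50% is an upper figure from another study. It does not close the gap, because each of these routes works by chance or is not connected to 23.1.

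Two other strong readings also go too far. Section 16.2 has identifiers destroyed at closure or publication, which might suggest that a death search would be impossible. The planned linkage itself needs identifiers, so nothing indicates they would be gone before it is requested. Section 20.6 might suggest that values will be carried past death. It only permits carrying forward, in analyses described as mainly descriptive.

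On importance, this is a single-arm feasibility pilot described as no more than minimal risk, and 23.1 already says its safety data cannot be examined statistically. That limits what can be inferred from the events; it is not a reason to leave a listed event unsought. Finally, some pages and the IRB application materials cited in section 28 are not visible, so a check could be described there.

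**Conclusion.** The point holds in a limited form. Followed as written, 23.1 cannot reliably find an event it says will be reviewed, and deaths among people lost to follow-up could be missed. The survey source could be silent for up to 30 of 60 people, or 45 of 90, at a visit, if attrition reaches the upper figure in 4.2. How many deaths that would hide, if any, cannot be estimated. The primary completion result does not change, and the linkage or site knowledge might reveal some deaths. What the study would lack is the ability to tell no deaths from deaths not looked for.

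The conclusion rests on the visible text and on reading 23.1's two sources as the ones planned for safety review. It is a worthwhile, inexpensive improvement and not a flaw that threatens the main result.

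**What to change.** 1. **Section 23.1.** When a 3- or 6-month survey is missed by someone who has not withdrawn, have existing staff use the contact methods already held and site knowledge to record vital status, with source and date, without disclosing study participation. State whether the partial withdrawals described in section 15 are included.
2. **Sections 13.2 and 13.3.** Name death records in the planned state linkage request. State that linked deaths, overdoses and hospitalisations feed a final retrospective safety review, within the limit that 19.4 sets for data after withdrawal. Reconcile the required wording in 13.2 with the permissive wording in 13.3.
3. **Reporting and section 20.6.** Report the number with unknown vital status at 3 and 6 months beside any count of deaths. As a secondary point, record death as its own reason for missing data and do not carry values forward past a known death.

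The cost is protocol wording, modest staff time and one more file in the governance-board and data use approvals. Contact attempts need care over confidentiality, because 9.1 says "the primary risks include being identified as a participant in this study". If the death file is refused or arrives late, items 1 and 3 can still be done.
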